6. GENERAL ANALYSIS DEFINITIONS

6.1 TREATMENTS

For the purposes of the statistical analyses, treatments will be referred to in the same context as in CTP Version 3 Section 7.4.

- “Alteplase”, which is alteplase 0.6 mg/kg over 2 hours followed by 0.04 mg/kg/h over 12 hours
- Standard of Care (SOC)

Alteplase treatment is planned to be up to end of Day 5 but all patients should be taking SOC in the background. On day 1 there is an initial 2 h infusion for all, followed up by a longterm 12 h infusion. On days 2-5 the patients can receive an optional 2h infusion (based on investigator decision), but only on one of these days. Each patient should receive a longterm 12h infusion on these remaining 4 days. Some patients may have a temporary interruption, as advised by CTP Version 3 Section 3.3.4.1.

6.2 IMPORTANT PROTOCOL DEVIATIONS

Patients with any of the following important protocol deviations (iPDs) will be reviewed on a case by case basis (5) and (6). The review of the iPDs will be used to determine criteria for a PPS.

Note that this is a working list and may be updated again prior to the final Report Planning Meeting (RPM) prior to the snapshot related to end of Part 2. Inclusion criteria/exclusion criteria numbers refer to the definition given in the CTP Version 3 or CRF.

Table 6.2: 1 Handling of iPDs

iPD code	iPD Category & Brief Description
A	Entrance Criteria Not Met
A1	Inclusion Criteria not met
A1.1	Patient too young (IC1)
A1.2	Diagnosis of ARDS questionable (IC2,4,5)
A1.3	Patient does not test positive for SARS-CoV-2 (IC3)
A2	Exclusion Criteria not met
A2.1	Patient has baseline conditions that are not permitted for safety reasons (EC1-33)

Table 6.2: 1 Handling of iPDS (continued)

iPD code	iPD Category & Brief Description
A2.2	Patient has baseline conditions that prevent patient from complying with study protocol (EC1-33)
A2.3	Patient has had previous conditions or procedures that are not permitted (EC1-33)
A2.4	Patient has had forbidden previous therapy (EC1-33)
A2.5	Patient pregnant (EC27)
B	Informed Consent
B1	Informed consent not available (IC6)
B2	Informed consent not signed at screening visit 1 (IC6)
B3	Informed consent not available or not available at visit 2a (pre-dose) (IC6)
C	Trial medication and randomisation
C1	Method of assigning patients to treatment arms
C1.1	Randomisation not followed according to protocol
C1.2	Patients do not receive the initial treatment they were randomised / allocated to
C1.3	Patient assignment not followed
C1.4	Timeframe > 1 day between randomisation and first drug intake
C2	Non-compliance
C2.1	Overall Compliance not between 80% and 120% inclusive – see definition in Section 5.4 .
C2.2	Patient takes the optional 2h infusion on more than one occasion after the initial 2h infusion.
C3	Drug assignment and administration of doses for each patient
C3.1	Dosage and treatment schedule not given according to protocol for initial iv infusion
C3.2	Dosage and treatment schedule not given according to protocol for long term iv infusion
C3.3	Drug not permanently discontinued according to CTP Version 3 Section 3.3.4.1
C3.4	Drug not temporarily interrupted according to CTP Version 3 Section 3.3.4.1

Table 6.2: 1 Handling of iPDS (continued)

iPD code	iPD Category & Brief Description
D	Concomitant medication
D1	Intake of restricted concomitant medication according to CTP Version 3 Section 4.2.2.1 and Section 10.2
D2	Intake of marketed Actilyse® (non-study drug) not as ultima-ratio or bail-out
G	Other trial specific important deviations
G1	Other protocol violations affecting patient rights or safety (manual PDs to be captured)

6.3 SUBJECT SETS ANALYSED

The subject sets as defined in CTP Version 3 Section 7 for the Randomised Set (RS), Full Analysis Set (FAS) and Treated Set (TS) will be used.

The Screened set (SCR), not outlined in the CTP Version 3, will include all patients screened.

The RS will consist of all randomised patients.

The FAS will consist of all randomised patients with at least one baseline and one post baseline assessment relating to the primary endpoint of interest. That is to say, they need to have at least one assessment post baseline on the 11-point WHO Clinical Progression Scale.

The TS will consist of all patients who were randomised and, for patients in the alteplase group, treated with at least one dose of trial drug.

[figure not shown]
Per Protocol Set (PPS) will consist of all patients in FAS who were without important protocol deviations (IPDs) for efficacy, as outlined in [Table 6.2: 1](#).

The Pharmacokinetic set (PKS), not outlined in CTP Version 3, will comprise all subjects in the TS who provided at least one PK endpoint and had no important protocol violations relevant to the evaluation of PK.

[Table 6.3: 1](#) below outlines which analysis set is to be used for the various endpoints or summaries.

Table 6.3: 1 Subject sets analysed

Class of endpoint	Subject set			PPS	PKS
	SCR / RS	TS	FAS		
Primary endpoint			primary and supplementary analyses	Primary analyses	
Key secondary endpoints			x	Primary analyses	
Other secondary EFFICACY and further EFFICACY endpoints			x		
Secondary SAFETY and further SAFETY endpoints		x			
Treatment exposure		x			
Disposition	x				
Demographic/baseline		x	x	x	
Concomitant medications and compliance		x	x		
All other safety analyses		x			
PK analyses					x

6.5 POOLING OF CENTRES

Part 2 of this study is planned to be carried out in approximately 110-130 centres in approximately 22 countries. However, not all centres have the same SOC procedures. During the course of the study, and gathering information (retrospectively) from each of the centres

with regard to their SOC procedures, they will be grouped into relatively homogeneous groupings. The same process as done for Part 1 will be carried out again for Part 2.

Because the groupings will only be made after randomisation of a patient within a centre, this will be a retrospective and exploratory analysis, albeit planned. It is planned only to investigate the primary endpoint with this centre grouping in a sensitivity analysis – see [Section 7.4.2](#).

6.6 HANDLING OF MISSING DATA AND OUTLIERS

All efforts will be made to avoid having missing data in the database, however it is inevitable that there will be missing data, by design:

- For patients that die, there will be no further data, however this irreversible unfavourable state will be taken into consideration in the determination of each of the endpoints.
- For patients that are discharged from hospital before day 28, the only additional efficacy assessment is the vital status at days 28 and 90. The fact that the patient has improved in order to be discharged from hospital prior to day 28 will be taken into account in the determination of each of the endpoints.

Handling of missing data for the endpoints are outlined in [Section 5](#), in line with the definitions of the endpoints.

Missing or incomplete adverse event (AE) dates will be computed using the BI handling rules ([7](#)).

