----------------------------	---

Clinical Trial Protocol

Page 7 of 140

Proprietary confidential information © 2022 Boehringer Ingelheim International GmbH or one or more of its affiliated companies

	
IMV cohort, adjustment will be made for the baseline WHO value, baseline D-Dimer level and age.
 
For each of the two key secondary endpoints, treatment failure at Day 28 and all cause mortality at Day 28, the delta method and average marginal effect method will be used to calculate the risk difference, 95% confidence intervals and p-values. Adjustment will be made for the same set of covariates as in the primary analysis of the primary endpoint.
 
Descriptive statistics will be used to analyse all other endpoints and for all analyses of the IMV patient cohort.
 
If the NIV and IMV patient cohorts show homogeneity, then a meta-analysis will be performed to obtain an overall treatment estimate, albeit in an exploratory manner.

--	---

Clinical Trial Protocol

Page 8 of 140

Proprietary confidential information © 2022 Boehringer Ingelheim International GmbH or one or more of its affiliated companies

FLOW CHART

Trial Periods	Screening	Intravenous open-label treatment					Follow-Up			
Visit number	1	2a	2b	2c	2d	2e / EOT	3	4	5	6 / EOS
Day	0	1	2	3	4	5	6	7	28	90
Hours	-24 - 0	0-14	26-38	50-62	74-86	98-110	134			
Time windows [hrs, if not specified otherwise]		+6	±2	±2	±2	+6	±12	+1 day	+2 days	±7 days
Informed consent (separate IC for patients participating in PK sampling)	X									
Demographics	X									
Medical history	X									
Physical examination	X					X			X	
Weight	X									
Height	X									
Vital signs ¹	X	X	X	X	X	X	X	X	X	
12-lead ECG ²	X	(X only needed in case of clinical event) ²								X
Review of in-/exclusion criteria	X									
IRT call	X	X				X				
Randomisation ³		X								
Dispense trial drugs	X									
Administer trial drug ⁴		X	X	X	X	X				
PK Sampling ⁵		X								
Laboratory Tests ⁶	X			X		X	X ⁶		X	
D-dimer assessment ⁷	X			X		X		X	X	
Fibrinogen, aPTT and antithrombin assessment ⁸	X	X	X	X	X	X	X	X	X	
PaO ₂ /FiO ₂ ratio (or inferred PaO ₂ /FiO ₂ ratio from SpO ₂) ⁹	X	X	X	X	X	X	X	X	X	

Trial specific examinations: SOFA score ¹⁰	X						X		X	
11-point WHO Clinical Progression Scale (see Section 5.1.1) ¹¹	X	X	X	X	X	X	X	X	X	
Pregnancy testing ¹²	X								X	
SARS-CoV-2 test ¹³	X									
All adverse events/Serious adverse events ¹⁴	X	X	X	X	X	X	X	X	X	
Concomitant therapy	X	X	X	X	X	X	X	X	X	

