8. During the treatment period, fibrinogen should be measured daily. The aPTT should be measured at least daily, but preferably more often. The aPTT (for all patients on unfractionated heparin [UFH]) or anti-Xa (for all patients on low-molecular weight heparin [LMWH]) should be used to check the intensity of anticoagulation. In patients with moderate (creatinine clearance 30-50 ml/min) and mild (creatinine clearance 50-80 ml/min) renal impairment, careful clinical monitoring of anticoagulation intensity according to institutional guidance is advised. (more details see [Section 4.2.1](#))
9. PaO₂/FiO₂ is only measured during hospital stay. The qualifying PaO₂/FiO₂ ratio should be the worst measurement in the screening period. During the treatment period the worst measurement on a given day should be documented in the case report form. During the first 6 days and during the stay on ICU (whatever is longer), PaO₂/FiO₂ ratio should be measured at least three times daily in all patients, together with a recording of the patient's position.
10. The SOFA score will be assessed at baseline, Day 6 and Day 28 (or just before hospital discharge whichever comes first including vital signs assessment and laboratory samples needed for score calculations. (Please refer to [Appendix 10.1](#)). If patient is discharged from hospital prematurely, last evaluation during hospital stay is expected at day of discharge from hospital.
11. WHO clinical progression scale should be collected daily during hospital stay. The last measurement on a given day should be recorded in the case report form. On Day 1 (randomisation day) an assessment just before randomisation shall be collected as a baseline value.
12. Only applicable for women of childbearing potential. Urine pregnancy test will be performed at screening and at Visit 5. Study drug should only be administered in case of a negative test result. A woman is considered of childbearing potential, i.e. fertile, following menarche and until becoming post-menopausal unless permanently sterile. Permanent sterilisation methods include hysterectomy, bilateral salpingectomy and bilateral oophorectomy. Tubal ligation is NOT a method of permanent sterilisation. A postmenopausal state is defined as no menses for 12 months without an alternative medical cause.

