5.1.2 Oxygen- free and Ventilator-free days, days in ICU

Oxygen-free and ventilator-free days until Day 28 will be captured from source documents. Time-points of intubation and extubation will be recorded in the eCRF. Days on ICU, intermediate care, step-down unit (normal ward) will be counted until Day 28 based on source documents. Date of discharge from hospital and/or death will be recorded in the eCRF.

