6. INVESTIGATIONAL PLAN

The trial consists of three periods, a screening period, an intravenous open-label treatment period and a follow-up period.

During the treatment period, patients will receive an open-label infusion with alteplase on top of SOC, or SOC alone.

Instructions on alteplase infusion dosage and treatment schedule is provided in [Table 4.1.4:1](#).

All required procedures are described in the [Flow chart](#) and [Section 5](#).

After completion of the treatment period patients will be followed-up on Day 6, Day 7, Day 28 and Day 90/EOS.

If patient is discharged from hospital before completion of Day 28, the patient has to be invited to complete subsequent visits as per [Flow chart](#) until Day 90 including vital status collection.

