10.4 POTENTIAL MODIFICATION OF TRIAL CONDUCT IN CASE OF RESTRICTIONS DUE TO COVID-19

Due to restrictions during the COVID-19 pandemic, study conduct may need to be adjusted.

In exceptional cases, when it is impossible to conduct the visits for discharged patients at the trial site, visits may be performed at the patient's home or remotely (via telephone and/or internet based means of communication). Based on the benefit-risk assessment (see [Section 1.4.1](#)), the visit procedures may be adjusted for the purpose of particular visits, whereby critical safety measures will remain in place. All home/remote visits need to be discussed with and approved by the sponsor's trial team. Local regulatory and legal requirements of the participating country need to be respected for all modifications.

Under these circumstances, the following modifications can be considered:

Remote visit

If a patient is not able to come to the site for an outpatient visit, a remote visit (by phone) should be performed instead and all assessments that can be done by phone should be performed.

Assessments that can be performed during a remote visit are:

Collection of adverse events, concomitant therapy, local laboratory. If home visits by trial staff members are possible, further assessments can be done.

Safety lab, other laboratory tests

Blood analysis for safety laboratory can be done in a local laboratory outside the hospital. The results of the laboratory tests are to be reported and transferred to the investigator, who has to ensure medical review and proper documentation in the eCRF.

Monitoring

Due to the nature of this trial and the risks associated with Covid-19, site monitoring visits as physical on-site interaction may not always be possible. The focus will be on centralized oversight/monitoring. If not restricted by local Covid-19 regulations, we recommend combination of remote and on-site visits, mainly for initiation and close-out visits. Regular interim monitoring visits will occur mainly remotely unless the trial team requires a visit to be done on-site due to an identified risk where the required mitigation may need to be performed on-site.

Trial monitoring intervals may be adjusted depending on enrolment rates, data quality, recruitment and conduct phases, timelines for CRF completion and/or site quality.

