5.2 SECONDARY ENDPOINTS

5.2.1 Key secondary endpoints

The two key secondary endpoints as defined in CTP Version 3 Section 2.1.3 will be analysed on the FAS, and these are both based on the daily assessment of the WHO Clinical Progression scale.

The planned analyses of the key secondary endpoints are outlined in [Section 7.5.1](#).

Treatment failure (ACM / MV) at day 28, FAS, binary endpoint

This unfavorable endpoint is met if:

- the last known status of the patient has a value of ≥ 7 on the WHO clinical progression scale, up to end of day 28, or
- vital status is dead within 28 days

ACM at day 28, FAS, binary endpoint

This unfavorable endpoint is met if:

- the last known status of the patient is 10 on the WHO clinical progression scale by the end of day 28, or
- vital status is dead within 28 days

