- If day 6 value is missing, no Day 5 value available, but day 7 available, then day 7 value will be used
- Otherwise value set to missing for that patient.

Based upon this, the change from baseline for each patient will be calculated and used for the analysis.

Number of oxygen-free days (OFD) up to day 28, FAS, continuous endpoint

For this endpoint, 'oxygen-free' is defined as free from assistance from oxygen support. The number of oxygen-free days starts from when the patient has a 'lasting' value on the WHO clinical progression scale of ≤ 4 and ends on Day 28. A lasting value of ≤ 4 means that the value cannot exceed 4 at a later timepoint. If the patient is liberated from oxygen on Day x, then the number of OFDs is 28-x. If a patient has withdrawn consent prior to day 28 then he will have a missing value for OFD. In any case, if the status of the patient at Day 28 is death, as determined from the vital status page then the OFD=0.

Length of hospital stay up to day 28, FAS, continuous endpoint

This will be determined based upon the first hospital discharge date, or discharge to another care facility. If the patient dies within the first 28 day period, then length of hospital stay is 28.

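### After discharge the Part 2 SAP uses only vital status, so non-fatal deterioration by Day 28 is missed in treatment failure and oxygen-free days, and hospital stay stops at first discharge or transfer

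*SAP*

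**What the plan says.** **Post-discharge data.** Part 2 SAP 6.6: "For patients that are discharged from hospital before day 28, the only additional efficacy assessment is the vital status at days 28 and 90". The same section says that improvement leading to discharge will be allowed for in each endpoint and refers to SAP Section 5 for the rules.

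**Treatment failure (H0_2).** Protocol 2.1.3 defines it as death or mechanical ventilation at Day 28. Part 2 SAP 5.2.1 counts a failure if "the last known status of the patient has a value of" 7 or more on the WHO scale up to the end of Day 28, or if the patient died within 28 days. It has no rule for patients discharged alive. The Part 1 SAP (5.2.2) assumed unknown ventilation status to mean not ventilated; the Part 2 SAP does not repeat this.

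**Oxygen-free days.** Part 2 SAP 5.2.2 counts 28 minus the day on which the WHO value falls to 4 or below and never rises above 4 again, and assigns 0 if the patient is dead at Day 28. Protocol 5.1.2 names a different source: "Oxygen-free and ventilator-free days until Day 28 will be captured from source documents".

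**Hospital stay.** Part 2 SAP 5.2.2: "This will be determined based upon the first hospital discharge date, or discharge to another care facility". Death within 28 days gives 28.

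**Protocol schedule.** The Flow chart row "11-point WHO Clinical Progression Scale (see Section 5.1.1") is marked at every visit up to Visit 5 (Day 28). Footnote 11 to that row says: "WHO clinical progression scale should be collected daily during hospital stay". Section 6 adds: "If patient is discharged from hospital before completion of Day 28, the patient has to be invited to complete subsequent visits". The remote-visit list in Appendix 10.4 leaves the scale out: "Collection of adverse events, concomitant therapy, local laboratory".

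**The concern.** An endpoint defined by status at Day 28 needs status at Day 28. For a discharged patient who is still alive, the SAP substitutes the status at discharge, so later readmission, ventilation or oxygen does not enter treatment failure or oxygen-free days. If alteplase leads to earlier discharge, as the primary hypothesis expects, that arm spends more time unobserved and could have more missed failures. The trial is open-label, and discharge and transfer are site decisions. The affected results are the second step of the confirmatory hierarchy and two non-confirmatory secondary endpoints.

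The documents also disagree on whether a discharged patient has a WHO score at Day 28. Sites could collect it for some discharged patients and not for others.

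**Working it through.** **1. Apply the SAP rules to example courses.** Where discharge occurs on Day 10, WHO 4 or below is taken as first reached that day.

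| Course | Treatment failure | Oxygen-free days | Hospital stay |
|---|---|---|---|
| Home Day 10, readmitted Day 15, alive and ventilated at Day 28 | No (actual status: yes) | 28 - 10 = 18 (lasting rule broken, but not observed) | 10; readmission days lost |
| Home Day 10, dies by Day 28 | Yes | 0 | 28 |
| Transferred Day 5 while ventilated, alive at Day 28, no later data | Yes (last value 7 or more) | None (no value of 4 or below) | 5; error up to 28 - 5 = 23 days |
| Transferred Day 5 at WHO 6, later ventilated, alive at Day 28 | No (missed) | None | 5 |

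The gap is non-fatal deterioration after discharge, plus the stay rule for transfer and readmission.

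**2. Reproduce the plan's figure for H0_2.** Inputs (Protocol 7.5): 70 SOC and 140 alteplase NIV patients, failure rates 40% and 20%, two-sided 5%.

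- Pooled rate: (28 + 28)/210 = 0.267.
- Standard error under the null: √[0.267 × 0.733 × (1/70 + 1/140)] = 0.0647.
- Standard error under the alternative: √[0.40 × 0.60/70 + 0.20 × 0.80/140] = 0.0676.
- Power: Φ[(0.20 - 1.96 × 0.0647)/0.0676] = Φ(1.08) = 86.0%.

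This lies within the stated 85-90%. The sample size calculation is not in error.

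**3. Illustrate the shift in the risk difference.** Let m be the share of discharged patients who are alive and ventilated at Day 28 but scored as non-failures. The documents give no value, so m is an assumption, taken as equal in both arms. Discharge is itself a primary event, so, apart from patients censored earlier at bail-out, the planned primary event rates (50% alteplase, 30% SOC) cap the discharged share in each arm. The calculation sets each arm at its cap.

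Missed share = 0.50m (alteplase) and 0.30m (SOC); shift = (0.50 - 0.30)m. Taking 40% and 20% as the scored rates:

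| m | Missed patients, alteplase / SOC | Corrected rates, SOC / alteplase | Risk difference | Shift towards alteplase | Power at corrected rates |
|---|---|---|---|---|---|
| 2% | 1.4 of 140 / 0.42 of 70 | 40.6% / 21.0% | -19.6 points | 0.4 points | 84% |
| 5% | 3.5 of 140 / 1.05 of 70 | 41.5% / 22.5% | -19.0 points | 1.0 points | 81% |

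**4. Limits of the illustration.** The caps bound the missed share in each arm, not the difference between arms. Direction depends on equal m: with 2% in alteplase and 5% in SOC the missed shares are 1.0% and 1.5%, and the shift is 0.5 points against alteplase.

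**The case against.** **Stronger readings that the documents do not support.** A reader might infer that a discharged or transferred patient is scored favourably whatever follows. That is wrong for death, which by Day 28 makes the patient a treatment failure, sets oxygen-free days to 0 and sets hospital stay to 28. A reader might also infer that transfer counts as discharge throughout. The SAP says so only for hospital stay. Nor is it established that home oxygen will be scored as oxygen-free: WHO levels 1-3 do not mention oxygen, but the SAP defines oxygen-free as without oxygen support and the protocol points to source documents.

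**The data may largely exist already.** The Day 28 visit is scheduled with the WHO scale, and discharged patients are invited. Footnote 11 is not limited to the first stay and could cover a readmission. The eCRF takes intubation and extubation times (Protocol 5.1.2), oxygen support dates are collected (6.2.2), and adverse events are collected to end of study (5.2.6.2.1). The remote-visit list is for exceptional cases. This makes the fix cheaper but does not close the gap: the SAP derives treatment failure from WHO values, not from these records, and 6.6 states that no efficacy assessment other than vital status follows discharge. Respiratory failure and ARDS progression are also exempt from SAE reporting (5.2.6.2.4), although recorded on the eCRF.

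**The size is assumed, and the stay rule is pre-specified.** Both are true. No document supports 2-5%, and the 23 days is one patient's maximum error, not a difference between arms. Pre-specification makes the stay rule transparent, but it still records a patient moved between hospitals on a ventilator as having left hospital.

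**Conclusion.** The point holds. Under the Part 2 SAP, readmission, ventilation or renewed oxygen after discharge is not counted in treatment failure or oxygen-free days when the patient is alive at Day 28. Readmission days and continued inpatient care elsewhere are lost from hospital stay. SAP 6.6 and footnote 11 conflict with the Flow chart's Day 28 WHO assessment and with the invitation of discharged patients to that visit.

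The size of any bias cannot be derived from the documents. On the stated assumptions it is about 0.4-1.0 points towards alteplase, against a planned -20. That alone is unlikely to reverse H0_2 if the planned effect is real. The reason to act is that stated rules misclassify identifiable patients on a confirmatory endpoint although a contact that could prevent this is already scheduled.

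**What to change.** 1. Reconcile SAP 6.6, footnote 11 and Appendix 10.4 with the Flow chart, so that the Day 28 WHO score is required for every surviving patient, whether in hospital or not.
2. At the scheduled Day 28 visit or phone contact, record for each discharged or transferred patient the WHO score, invasive ventilation on Day 28, oxygen use and readmission dates.
3. Score treatment failure and oxygen-free days from these data, and state in SAP Section 5 what is assumed when Day 28 status cannot be obtained.
4. For length of stay, count days in another acute-care hospital and readmission days up to Day 28.

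**Cost.** A few CRF items, SAP wording and a protocol clarification, with no new visit. Some data will be incomplete where outside records cannot be obtained or a phone report cannot be verified, and chasing records across 110-130 planned sites takes effort. The Part 2 SAP needs revision anyway: it follows Protocol Version 3 and still uses D-dimer strata starting at 3-fold ULN, whereas the current protocol starts at ULN. The collection change is the urgent part, because Day 28 status is harder to recover once the contact has passed.
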